9.2 Sample Size and Randomization

Based on the projected enrollment numbers, there is ample power to detect a statistically significant difference between the intervention and control groups with regards to the primary aim of hospitalization and ED visit rates. To determine this, we used data from a recent national study conducted between 2009-2012.⁵³ These results demonstrated that the rate of ED visits after transplant was 1.269 per person-year and 48% of those ED visits resulted in hospitalization. We will enroll 10 sites (5 sites for each study arm) and will have a total of just more than 1,600 patients that are roughly split between the intervention and control sites. We used a conservative estimate of an intra-cluster correlation of 0.05 and calculated a sample size of 1,350 to allow us to detect a 25% relative decrease in ED visit and hospitalization rates with 80% power. The 25% relative improvement in rates is a conservative estimate of intervention effect, based on previous pharmacist-led initiatives the investigators have conducted.^{15,16} After allowing for 15% loss to follow up, we require a total of 1,600 to meet study power. We expect to have 1,689 patients based on site estimates. These power calculations were conducted using a two-sided test for counts with Poisson regression adjusting for intra-cluster correlation and with alpha set at 0.05.

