9.4 Data Analyses

The data analysis will incorporate the intent-to-treat principle; namely, all participants enrolled in the intervention group will be included in the analysis and compared to all of the patients captured within the control group. If a patient dies, has graft loss or moves out of their study site, their data will be censored at that time point. For comparative statistical assessments within the utilization outcomes, the two groups will be compared using a generalized linear mixed models (GLMM) approach.⁵⁴ This approach allows for measurement of participants at different time points, clustering by study site, missing data under the assumption of missing at random (MAR), time varying or invariant covariates, and can also account for the effect of correlated longitudinal measurements within participants. In addition, GLMM accommodates a wide range of distributional assumptions such as dichotomous (e.g. binomial), count (e.g. Poisson), continuous

(e.g. Gaussian), and categorical or ordinal outcomes. For comparing the primary outcome (ED visit and hospitalization rates), we will use GLMM (with appropriate link function) with counts of these events as the outcome variable and intervention group (yes/no) as the primary independent variable. This analysis is equivalent to Poisson regression or negative binomial regression (in the case of over-dispersion), both special cases of GLMM. Additional adjustment covariables will be added to the model in a second set of analyses. Covariates will include patient sociodemographics: age, sex, race, comorbidities (using modified Elixhauser definitions), marital status and education. In these models, donor information (age, sex, race, deceased or living) and transplant characteristics (HLA mismatches, ischemic times, panel reactive antibody levels, time since transplant) will also be included. This will assist in making valid intervention effect estimates after accounting for baseline differences, as there may be patient-level differences between groups. The magnitude of between intervention differences on outcome variables (effect sizes) at each time point will be estimated using appropriate contrasts in the corresponding GLMM models.

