We anticipate that some of the count outcomes will exhibit excess zeros (e.g. hospitalizations). If the counts exhibit excess zeros, we will use zero-inflated (ZI) versions of the proposed model (zero inflated Poisson and zero-inflated negative binomial [NB]) to account for the excess zeros with random effects to account for clustering by site.⁵⁵ Typically, Poisson regression is used to model count data where observations are assumed to be independent and the number of cases has variance equal to the mean for each level of the covariates. However, in practice, either the independence or equal mean and variance assumption is often violated, which can lead to over-dispersion (when the variance is greater than the conditional mean). Thus, we consider a NB model that handles the problem of over-dispersion and that does not assume an equal mean and variance assumption. In certain cases, over-dispersion may not be sufficiently modeled via the extra parameter in NB. In this case we will consider including random effects into the NB model. Zero inflated models such as ZINB can be used for modeling the excess zeros. The ZINB model is a mixture of NB model for the count part and a logit model for the excess zeros. The parameters in the ZINB model have conditional or latent class interpretations, which correspond to a susceptible subpopulation at risk for the condition (in our case ED visits/hospitalizations) with counts generated from a NB distribution and a non-susceptible subpopulation that provides the extra or excess zeros. Thus, the ZINB model parameters are not well suited for quantifying the effect of an explanatory variable in the overall mixture population. We will use a marginalized ZINB model to estimate the population mean count directly, allowing straightforward inference for overall covariate effects.⁵⁶ We will use AIC and BIC, which deal with the trade-off between the goodness of fit and complexity of the models, to choose the best fitting model among the different models; further assessment of the goodness of fit for the final model is made via the Pearson goodness of fit statistic. A model with a smaller value of AIC, BIC, and a Pearson statistic close to one is considered a better fit of the data. We will use SAS 9.4, housed within the VINCI environment, to manage the data and fit all the models.

For the cost analysis, we will also utilize multivariable modelling and propensity score

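### Section 9.4 does not require a site random effect in the negative binomial primary model; if it is left out, type I error is about 46–53% at the plan's ICC of 0.05

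*Combined protocol and SAP*

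**What the plan says.** Section 9.4 (Data Analyses) compares utilization outcomes with a generalized linear mixed model and lists clustering by site among the features this approach can handle. It does not write out a random-effects structure. It then describes the primary analysis this way: "This analysis is equivalent to Poisson regression or negative binomial regression (in the case of over-dispersion), both special cases of GLMM".

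If there are excess zeros, zero-inflated versions are to be used, and for these random effects for site are stated outright. For the NB model without zero inflation, the only sentence on random effects applies when the NB dispersion parameter leaves over-dispersion unexplained: "In this case we will consider including random effects into the NB model".

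AIC and BIC choose among the models, and the Pearson statistic is a further check on the model chosen: "A model with a smaller value of AIC, BIC, and a Pearson statistic close to one is considered a better fit of the data".

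Section 9.2 (Sample Size and Randomization) does build clustering in: "We used a conservative estimate of an intra-cluster correlation of 0.05". The calculation is described as a "two-sided test for counts with Poisson regression adjusting for intra-cluster correlation and with alpha set at 0.05". No small-sample method for 10 sites appears in either section.

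**The concern.** Sites are the randomised units, so whether the primary test accounts for site should follow from the design and not from a diagnostic. In the NB branch, the only stated route to a random effect depends on residual over-dispersion and even then is discretionary. Residual over-dispersion is the wrong signal. Differences between sites look like extra variance between patients, which the NB dispersion parameter is built to soak up. An analyst could follow the text, see a well-fitting NB model, and report a test that treats more than 1,300 patients as independent when the evidence on the intervention comes from 10 sites. The confidence interval would be far too narrow, and an intervention with no effect would often appear beneficial or harmful.

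**Working it through.** **Inputs.** From section 9.2: control rate 1.269 per person-year, rate ratio 0.75, two-sided alpha 0.05, 80% power, ICC 0.05, 10 sites with 5 per arm, 1,350 evaluable (135 per site), 15% loss, 1,689 expected (about 169 per site). From section 3: 24 months of follow-up, so the control mean is 2 × 1.269 = 2.538 events. Assumptions, because the documents give no figure: patient-level variance-to-mean ratios of 2 and 4 in the main simulations, and ICCs below 0.05.

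**Step 1: the plan's sample size.** Design effect (DEFF) = 1 + (135 − 1) × 0.05 = 7.70. On the log rate-ratio scale, n per arm before clustering = (1.960 + 0.842)² × [1/2.538 + 1/(0.75 × 2.538)] / (ln 0.75)² = 87.2. The total is 2 × 87.2 × 7.70 ≈ 1,343. The rate-difference form gives 1,334. Both agree with the stated 1,350, and 1,350/0.85 ≈ 1,589 agrees with 1,600. The plan's size therefore depends on a nearly eightfold variance inflation for clustering.

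**Step 2: error if the test ignores site.** Without a site term the squared standard error is too small by the factor DEFF, so type I error = 2 × [1 − Φ(1.96/√DEFF)].
- ICC 0.05, 135 per site: 1.96/√7.70 = 0.706, giving 48.0%.
- ICC 0.05, 169 per site: DEFF = 9.40, giving 52.3%.
- ICC 0.01, 135 per site: DEFF = 2.34, giving 20.0%. With 169 per site, DEFF = 2.68, giving 23.1%.

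**Step 3: simulation.** Null trials with 10 sites, mean 2.538, log-normal site effects scaled to the ICC, and NB fitted by maximum likelihood with and without a site random intercept. There were 300 to 600 trials per setting. With 400 trials the simulation standard error is about 2.5 points near 50% and 1.6 points near 12%.

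| ICC | No site term, formula | No site term, simulated | Site model chosen by AIC / BIC | Error after AIC or BIC selection |
|---|---|---|---|---|
| 0.05 | 48–52% | 46–53% | 96–100% / 89–95% | 11–16% |
| 0.02 (assumed) | 31–35% | 27–34% | 80% / 51% | 11–17% |
| 0.01 (assumed) | 20–23% | 16–25% | 47–49% / 18% | 10–21% |

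**Step 4: would the stated trigger fire?** Pearson/df for the NB model without a site term averages 1.00 to 1.03 across these settings. The check passes while the test is invalid.

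**Step 5: site intercept always included, ICC 0.05.** A Wald z test rejects in 11–14% of null trials. Referring the same statistic to t on 8 df gives about 6–7%. A t test on log site means, as a benchmark, gives about 5%. Most of the error left after AIC selection at ICC 0.05 therefore comes from the z reference with 10 sites, and the rest from trials where selection drops the site term.

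**Step 6: power on 8 df.** With 1,350 patients, SE = √[(1/1.269 + 1/0.95175)/(2 × 675/7.70)] = 0.1024, and 0.2877/0.1024 = 2.81. Against 1.96, power is Φ(0.85) = 80%. Against the 8-df critical value of 2.306, the non-central t gives about 69%.

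**The case against.** The documents show an intent to model site. Section 9.4 names a mixed model for the primary outcome, presents the zero-inflated fits with site random effects as versions of that model, and in its missing-data paragraph calls the proposed models mixed-effects models. Section 9.2 sizes the trial for clustering. The conditional sentence does not mention site and may concern additional patient-level effects.

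AIC and BIC are likelihood-based and do respond to a site effect when a model containing one is fitted. At ICC 0.05 they choose it in roughly 90% or more of trials. The Pearson statistic comes second, as a check on the chosen model, so only a disagreement between AIC and BIC lacks a rule. The plan also calls its ICC conservative.

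Most of this stands. A reader might infer that the plan discards the unit of randomisation, that its selection criteria cannot see clustering, and that the primary test will run at about 50% error. The documents support none of these. The 50% figure applies only if the site term is omitted and the ICC is 0.05.

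The objection does not supply a commitment. Saying that a model class can handle clustering does not specify a site term. If the conditional sentence is about patient-level effects, the ordinary NB model has no explicit site rule at all. A random-effects NB enters only after plain NB is judged inadequate, so AIC and BIC may never be given it to compare.

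**Conclusion.** The specification is inconsistent and not binding on a matter that decides whether the primary test is valid. It should be settled before the outcome data are analysed. Omitting the site term gives about 46–53% type I error at the plan's ICC and roughly 16–25% at ICC 0.01. Leaving the choice to AIC or BIC with both models fitted gives about 11–16% at ICC 0.05 and 10–21% at ICCs of 0.01 to 0.02, still at least twice nominal. The 46–53% is a conditional worst case, not the expected error of the plan. The sizes rest on equal site sizes, log-normal site effects and assumed patient-level dispersion. The formula in step 2, which needs no dispersion assumption, agrees closely at ICC 0.05.

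**What to change.** In section 9.4, replace the conditional sentence with three statements:

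1. Every candidate primary model (Poisson, NB and the marginalized zero-inflated versions) includes a random intercept for site, in both the unadjusted and the covariate-adjusted analyses.
2. AIC and BIC choose only the count distribution, with one named as decisive if they disagree. They never decide whether site is modelled.
3. The arm effect is tested on site-level degrees of freedom, 10 − 2 = 8.

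There is no need to fix NB in advance as the only distribution. The defect is the missing site term and reference distribution.

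This is a change of wording and needs no new data. The price is a wider interval and less power: on the plan's own inputs about 69% on 8 df, against the 80% obtained with a z test. The z-test figure overstates what 10 sites can deliver, because that test does not hold its 5% level. Error of about 6–7% remains slightly above nominal, so a site-level t test on log rates, at about 5%, would be a useful supporting analysis.

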9.3.2 Secondary outcomes

Secondary assessment will include a cost benefit analysis. Overall health care costs accrued during the 24-month study, as well as those accrued in the 24-months prior to study initiation will be analyzed and compared between the control and intervention groups. Cost data will be standardized using the VA Health Economics Resource Center (HERC) definitions, which normalizes regional differences in costs due to variation in cost of living indices. As with the primary outcome, we will also acquire and link CMS claims data to gain a comprehensive assessment of costs, including those that accrue from non-VA care (after study completion). Costs will also be sub-analyzed into three predominant categories: inpatient costs, outpatient costs and pharmacy costs, as described in the statistical analysis plan. To fully assess if the intervention is has a direct monetary benefit, we will measure costs of the intervention will include estimates of time and resources to implement the dashboard and train and support the intervention site pharmacists. Similar to primary outcome, we expect that as ER visits and hospitalizations decrease within the intervention arm, there will be a corresponding decrease in overall costs as well, predominantly driven by inpatient costs. We expect this decrease to occur during the second 12 months of the study period, as the intervention is likely to have a lag effect on this outcome as well.

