calibration (PSC).⁵⁷ We will assess the effect of the intervention on different sources of cost which include inpatient, outpatient and pharmacy in addition to the total aggregated cost. The cost models will be estimated using log-normal or gamma models (special cases of GLMM) to examine the association of the intervention with cost, adjusting for the aforementioned patient sociodemographics, donor information and transplant characteristics. Cost will be obtained from VINCI CDW and HERC as inpatient, outpatient, pharmacy and total aggregate for two years prior to the study period and for the two years of the intervention. We will also account for non-VA costs through linkage with CMS claims data. We will estimate different models adjusting for the clinical outcomes in order to examine the robustness of the results. GLMM allows for correlation between cost categories as well as for the likely skewed distribution of cost data. The Park test will be performed to check for the appropriate distribution of the cost data and AIC and BIC statistics for goodness of fit. Since, inpatient cost could exhibit a point mass of zero, we will use marginalized two-part models that are appropriate for semi-continuous data to model the relationship between the intervention and inpatient cost.^{58, 59} In general, statistical analyses will use two-sided tests with alpha set at 0.05.

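### The cost models have no stated target: if log-normal is chosen for total, outpatient or pharmacy cost, the arm effect is a ratio of geometric means, while the cost-benefit analysis needs arithmetic means

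*Combined protocol and SAP*

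**What the plan says.** Section 9.4 (Data Analyses) covers four cost outcomes, "which include inpatient, outpatient and pharmacy in addition to the total aggregated cost". On the model it says: "The cost models will be estimated using log-normal or gamma models (special cases of GLMM". On the choice between the two it says: "The Park test will be performed to check for the appropriate distribution of the cost data", and it adds AIC and BIC for goodness of fit. It expects skewness: the mixed-model approach is said to allow for correlation between cost categories "as well as for the likely skewed distribution of cost data". Because inpatient cost may have many zeros, that component is treated separately: "we will use marginalized two-part models that are appropriate for semi-continuous data".

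Section 9.3.2 (Secondary outcomes) says what the result is for: "Secondary assessment will include a cost benefit analysis". To learn whether the intervention "has a direct monetary benefit, we will measure costs of the intervention" as well. It expects that "there will be a corresponding decrease in overall costs as well, predominantly driven by inpatient costs". Total 24-month cost is the listed secondary objective in the synopsis.

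Neither section states whether the arm effect is to be a ratio or a dollar difference, or whether it refers to arithmetic or geometric means. The gamma link is not given, and there is no retransformation step for the log-normal model.

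**The concern.** A budget comparison sets saved dollars against spent dollars. Total spend is mean cost times number of patients, so the relevant quantity is the arithmetic mean. A gamma model describes that mean directly and, with a log link, gives the ratio of arithmetic means. A log-normal model describes the mean of log cost, so its exponentiated arm coefficient is a ratio of geometric means. A plan that lets fit statistics choose between them, with no retransformation stated, lets the data choose which quantity is reported.

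The plan accepts the principle elsewhere. For zero-heavy counts, section 9.4 adopts a marginalized zero-inflated model so that the population mean is estimated directly, and it uses a marginalized model for inpatient cost. Total, outpatient and pharmacy cost get no such protection. At stake is the total-cost effect that would naturally be compared with the cost of the dashboard and the pharmacists' time.

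**Working it through.** The documents state no cost effect, cost mean, cost SD or power for cost, so there is no figure of the plan's to reproduce. The check is analytic, followed by an illustration.

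**1. The two ratios.** For log-normal cost with log-scale mean m and log-scale SD s, the arithmetic mean is exp(m + s²/2). With s0 for control and s1 for intervention:

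geometric ratio = arithmetic ratio × exp((s0² − s1²)/2)

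- Equal log-SDs: the exponential is 1 and the ratios are identical.
- True saving 10% (ratio 0.90), s0 = 1.00, s1 = 0.95: 0.90 × exp((1 − 0.9025)/2) = 0.90 × 1.050 = 0.945. The reported saving is 5.5%, so 45% of it is missed.
- True saving 10%, s0 = 1.00, s1 = 1.05: 0.90 × exp((1 − 1.1025)/2) = 0.90 × 0.950 = 0.855. The reported saving is 14.5%, an overstatement of 45%.

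A 5% difference in log-SD is therefore enough to matter, in either direction.

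**2. Inputs for the illustration.**

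- From section 9.2: 1.269 ED visits per person-year, 48% leading to admission, and a 25% relative reduction.
- From section 2.1: the cost of readmissions linked to medication errors, given as more than $18,000 per case. It is used here as an assumed mean cost per admission.
- Assumed, not in the documents: mean non-inpatient cost $30,000 over 24 months with log-SD 0.6 to 1.2; admission-cost log-SD 0.8; gamma-distributed frailty in admission rates with variance 0 to 2; the 25% cut either uniform or confined to the quarter of patients with the highest admission rates.

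**3. True saving.**

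- Admissions per patient: 1.269 × 0.48 × 2 = 1.218.
- Inpatient mean: 1.218 × $18,000 = $21,928.
- Control mean: $30,000 + $21,928 = $51,928.
- Saving: 0.25 × $21,928 = $5,482, or 5,482/51,928 = 10.6% (arithmetic ratio 0.894).

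**4. What the geometric ratio reports.** Large-sample simulation, without covariates or site effects:

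| Non-inpatient log-SD | Frailty variance | Where the cut falls | Share of the percentage saving missed |
|---|---|---|---|
| 0.6 | 2 | top quarter | about 36% |
| 0.6 | 2 | uniform | about 25% |
| 0.6 | 1 | top quarter | 26% |
| 0.6 | 1 | uniform | 14% |
| 0.6 | 0.5 | top quarter | 16% |
| 0.6 | 0.5 | uniform | 7% |
| 0.6 | 0 | uniform | about 3% overstated |
| 0.9 | 1 | uniform | 2% |
| 1.2 | 0 | uniform | about 43% overstated |

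At the extremes, a true 10.6% saving would be reported as about 10.6% × 0.64 = 6.8% or 10.6% × 1.43 = 15%.

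**5. A second grid.** Another 24 scenarios used a median non-inpatient cost of $10,000 to $60,000 with log-SD 0.6 or 0.9, admission-cost log-SD 1.0 and a uniform cut. Results ran from 36% overstated to 34% missed. About a quarter or more was missed in only 3 to 4 of the 24, all with strongly over-dispersed admissions.

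**The case against.** The case on the other side has five parts.

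- **Common variance.** An ordinary log-normal model assumes one log variance for both arms, and then the two ratios coincide. That is correct, but equality is an assumption of the model. Nothing in the plan checks it or says what happens if it fails.
- **Inpatient cost is already on the mean scale.** This stands, and it matters, because section 9.3.2 expects the saving to arise mainly there. It does not extend to total cost, which is the stated secondary objective and would be the natural input to the cost-benefit comparison.
- **A log-normal fit can still yield arithmetic means.** Also true, once its variance is used arm by arm. The plan does not rule this out; it omits it. Nor does any section say that the cost-benefit figure will be a log-normal coefficient multiplied by mean cost. The link is a gap in the plan, not a stated error.
- **Gamma is not the only valid choice.** Agreed. Log-normal with arm-specific retransformation also targets the mean.
- **The size cannot be read from the documents.** This stands too.

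A reader might infer that the plan will understate the saving, perhaps by a quarter or more, because inpatient savings trim the upper tail and so shrink the log variance in the intervention arm. The documents do not support that. They give no cost distribution, say nothing about how the log variance would move, and do not say that the effect falls on frequent users. A shortfall of a quarter or more needs strong over-dispersion in admissions, a concentrated effect, or both; other plausible inputs overstate the saving.

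**Conclusion.** The gap is real for total, outpatient and pharmacy cost. Followed as written, the plan could report a ratio of geometric means where the cost-benefit question calls for arithmetic means, and fit statistics would decide which. Inpatient cost is not affected.

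Neither the direction nor the size can be fixed from the documents. Under the inputs listed above, the log-normal ratio ranges from overstating the percentage saving by about 43% to missing about 36% of it, and there is no error when the log variances are equal. If the ratio were applied to the control mean, a true saving of $5,482 per patient would read as about $7,840 (5,482 × 1.43) or $3,510 (5,482 × 0.64). These figures illustrate sensitivity and do not predict the trial's result. The outcome is secondary and the remedy is a matter of wording, so this is a cheap improvement to make before the cost data are analysed. It does not affect the primary analysis.

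**What to change.** Add to section 9.4:

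- The estimand for total, outpatient and pharmacy cost is the difference and the ratio in arithmetic mean 24-month cost between arms.
- One prespecified model on the mean scale estimates it, for example gamma with log link and a site random effect, or a marginalized two-part model where zeros occur.
- A log-normal model is used only as a sensitivity analysis, with retransformation by arm-specific variance.
- The Park test informs the variance function of the mean model and does not decide what is estimated.

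The cost is a few sentences of SAP text and no new data. The downside is a possible small loss of efficiency, not quantified here, if costs are truly log-normal with equal log variances in the two arms.
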